3.4 Safety Endpoints

The following endpoints will be included in the safety analyses:

- Treatment emergent adverse events (TEAEs);
- Serious adverse events (SAEs);
- Adverse events of special interest (AESIs);
- Adverse events (AEs) leading to discontinuation of study drug;
- Vital signs and laboratory tests.

4.0 Analysis Populations

Significant non-compliance was identified at an investigational site (Investigator ID [REDACTED]). As a result of this finding, efficacy data for the subjects enrolled at this investigational site will be excluded from the statistical analyses. Safety data for those subjects will be included in the statistical analyses. There was 1 subject enrolled at this site in the Induction Study.

Intent-to-Treat (ITT) Populations

The ITT population for the 8-week DB induction period (Part 1) (denoted by **ITT1**) includes all randomized subjects who received at least one dose of double-blinded study drug in Part 1. The ITT1 population will be used for all efficacy and baseline analyses for Part 1.

The ITT population for the 8-week OL extended treatment period (Part 2) (denoted by **ITT2**) includes all subjects who received at least one dose of upadacitinib 45 mg QD in Part 2.

For ITT1 population, subjects will be included in the analysis according to the treatment groups that they are randomized to.

Safety Populations

The safety population for Part 1 (denoted by **SA1**) includes all randomized subjects who received at least one dose of study drug in Part 1.

The safety population for Part 2 (denoted by **SA2**) includes all subjects who received at least one dose of the upadacitinib 45 mg QD in Part 2.

The all upadacitinib treated safety population (denoted by **SA-UPA**) includes all subjects who received at least one dose of upadacitinib in Part 1 or Part 2.

For the safety populations, subjects are assigned to a treatment group based on the "as treated" treatment group, regardless of the treatment randomized. The "as treated" will be determined by the most frequent dose regimen received in the analysis period.

5.0 Subject Disposition

A summary of subject accountability will be provided where the number of subjects in each of the following categories will be summarized for each treatment group:

- Subjects randomized in Part 1;
- Subjects who took at least one dose of study drug (Part 1 and Part 2);
- Subjects who completed protocol-specified treatment (Part 1 and Part 2);
- Subjects who prematurely discontinued study drug (Part 1 and Part 2);
- Subjects who prematurely discontinued from study.

Number and percentage of subjects who discontinued study drug and who withdrew from the study will be summarized by reason (primary reason and all reasons) for each treatment group within Part 1 and Part 2. Subjects with multiple reasons for premature discontinuation will be counted once in the calculation of the number and percentage of total discontinuations.

6.0 Study Drug Duration and Compliance

For the safety populations (SA1 and SA2), duration of treatment will be summarized for each treatment group. Duration of treatment is defined for each subject as last dose date minus first dose date + 1. Duration of treatment will be summarized using the number of subjects treated, mean, standard deviation, median, minimum and maximum. In addition, the number and percentage of subjects in each treatment duration interval (≥ 2 weeks, ≥ 4 weeks, ≥ 6 weeks, ≥ 8 weeks) will be summarized.

Treatment compliance will be summarized for each treatment period by treatment group. Treatment compliance is defined as the number of tablets actually taken divided by the number of tablets that should have been taken. Percent compliance will be summarized.

7.0 Demographics, Baseline Characteristics, Medical History, and Prior/Concomitant Medications

Demographics, Baseline or disease characteristics, medical history, and prior and concomitant medications will be summarized for the ITT1 population overall and by treatment group. Categorical variables will be summarized with the number and percentage of subjects; percentages will be calculated based on the number of non-missing observations. Continuous variables will be summarized with descriptive statistics (number of non-missing observations, mean and standard deviation, median, minimum and maximum).

7.1 Demographics and Baseline Characteristics

Continuous demographic variables include age, weight, height, and body mass index (BMI). Categorical demographic variables include:

- Sex (Male, Female)
- Age Group 1 (< 18 year, ≥ 18 years – < 40 years, ≥ 40 years – < 65 years, ≥ 65 years)
- Age Group 2 (≤ median, > median)
- Weight Group (≤ median, > median)
- BMI Group (normal: < 25 kg/m², overweight: ≥ 25 – 30 kg/m², obese: ≥ 30 kg/m²)
- Ethnicity (Hispanic or Latino, not Hispanic or Latino)
- Race (White, Black/African American, American Indian/Alaska Native, Native Hawaiian or Other Pacific Islander, Asian, Other)
- Region (US, ex-US)
- Tobacco user (current, former, never, unknown)
- Alcohol user (current, former, never, unknown)

Continuous baseline or disease characteristics variables include:

- Weight (kg)

- Height (cm)
- BMI (kg/m²)
- Disease duration (years)
- Full Mayo score and its components (stool frequency, rectal bleeding, Physician Global Assessment, and endoscopy subscores)
- Partial Mayo score
- Adapted Mayo score
- hs-CRP (mg/L)
- Fecal Calprotectin (µg/g)
- IBDQ total and domain score
- Short Form 36 Health Survey (SF-36) and its components
- European Quality of Life 5 Dimensions 5 Levels (EQ-5D-5L)
- Functional Assessment of Chronic Illness Therapy-Fatigue (FACIT-F)
- WPAI and its components
- Ulcerative Colitis Symptoms Questionnaire (UC-SQ)

Categorical baseline or disease characteristics variables include:

- Bio-IR status (Bio-IR, non-Bio-IR),
- Prior exposure to biologic therapy (yes, no) for non-Bio-IR
- Number of prior biologic treatments (≤ 1 or > 1) for Bio-IR
- Prior exposure to anti-TNF (yes, no)
- Baseline corticosteroid use (yes, no)
- Baseline immunosuppressant use (yes, no)
- Baseline aminosalicylates use (yes, no)
- Baseline Adapted Mayo score (≤ 7 , > 7)
- Baseline Full Mayo score (≤ 9 , > 9)
- Baseline hs-CRP (≤ 5 mg/L and > 5 mg/L)
- Disease duration Group 1 (≤ 3 years, > 3 years)
- Disease duration Group 2 (\leq median, $>$ median)

- Disease extent (rectosigmoid, left-sided, extensive/pancolitis)

7.2 Medical History

Medical history data will be coded using the Medical Dictionary for Regulatory Activities (MedDRA). The actual version of the MedDRA coding dictionary will be noted in the statistical tables and clinical study report. The number and percentage of subjects in each medical history category (by MedDRA system organ class and preferred term) will be summarized overall and by treatment group. The system organ class (SOC) will be presented in alphabetical order, and the preferred terms will be presented in alphabetical order within each SOC. Subjects reporting more than one condition/diagnosis will be counted only once in each row (SOC or preferred term).

7.3 Prior and Concomitant Medications

Prior and concomitant medications will be summarized by generic name (ITT1 population for prior medication; ITT1 and ITT2 populations for concomitant medications). A prior medication is defined as any medication taken prior to the date of the first dose of study drug in Part 1. A concomitant medication is defined as any medication that started prior to the date of the first dose of study drug and continued to be taken after the first dose of study drug or any medication that started on or after the date of the first dose of study drug, but not after the date of the last dose of study drug + 1 day. The number and percentage of subjects taking medications will be summarized by generic drug name based on the World Health Organization (WHO) Drug Dictionary for both prior and concomitant medications.

8.0 Efficacy Analyses

8.1 General Considerations

The efficacy analyses for the 8-week DB induction period (Part 1) will be conducted in the ITT1 population. The efficacy analyses for the 8-week OL extended treatment period (Part 2) will be conducted in the ITT2 population. All tests will be at the α level of 0.05

(2-sided). "Baseline" refers to the last non-missing observation prior to the first administration of the study drug or prior to the randomization if no study drug is given.

The primary analysis will be performed after all ongoing subjects have completed the study activities up to Week 16 and the database has been locked. This will be the only and final analysis for the primary and secondary efficacy endpoints as well as all other efficacy endpoints in the Induction Study.

Unless otherwise specified, categorical variables will be analyzed using Cochran-Mantel-Haenszel (CMH) test, stratified by bio-IR status (bio-IR vs. non-bio-IR), Baseline corticosteroid use (yes vs. no) and Baseline Adapted Mayo score (≤ 7 vs. > 7). Any subject who was randomized under the wrong stratum will be analyzed according to the actual stratum the subject belongs to. Continuous variables collected longitudinally will be analyzed using Mixed-Effect Model Repeat Measurement (MMRM) method. Continuous variables collected at only one post-baseline visit (such as Mayo score) will be analyzed using an Analysis of Covariance (ANCOVA) model.

8.2 Handling of Potential Intercurrent Events

Potential intercurrent events considered in the Induction Study include 1) premature discontinuation of study drug and 2) initiation or dose escalation of UC-related corticosteroids defined in Section 8.2.2. Intercurrent events will be handled using the following methods for the efficacy analysis:

8.2.1 Premature Discontinuation of Study Drug

Data collected will be used regardless of premature discontinuation of study drug.

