5.2.3.2 Concomitant Therapy

Concomitant UC-Related Medications (Oral Corticosteroids, Antibiotics, Aminosalicylates, and/or Methotrexate):

Substudies 1 and 2

All UC-related concomitant medications should be kept on the stable dose in Substudies 1 and 2. Dose may be decrease or terminated in the event of moderate-to-severe treatmentrelated toxicity (e.g., leukopenia or elevated liver enzymes) in the opinion of the investigator.

Substudy 3

At Baseline of Substudy 3 (Week 8 or Week 16 of Study M14-234 Substudy 1, Substudy 2, and Study M14-675), subjects who are taking corticosteroid therapy will have their corticosteroid therapy tapered according to a proposed tapering schedule specified in Section 5.3.1.1 in the Protocol. Subjects taking corticosteroids who have worsening of disease per the investigator's judgment after the steroid taper has been initiated may have their corticosteroid dose increased per the investigator's discretion during the study. Use of inhaled or topical dermatologic corticosteroids is not restricted.

All subjects receiving UC-related antibiotics may discontinue treatment starting at Week 0 of Substudy 3 at the discretion of the investigator.

All subjects receiving stable dose of UC-related antibiotics (those subjects who did not discontinue), aminosalicylates, or MTX at Week 0 will maintain their concomitant treatments and respective doses through the end of the study. Dose may be decreased or terminated in the event of moderate to severe treatment related toxicity (e.g., leukopenia or elevated liver enzymes) in the opinion of the investigator.

Changes in all concomitant medications will be assessed at each study visit from Baseline (Week 0) through Week 8/PD Visits in Substudies 1 and 2 or Study M14-675; through Week 16/PD Visits in the extended treatment periods of Substudy 2 or Study M14-675; and through Week 52/PD Visits in Substudy 3. Any changes will be documented in the source documents and captured on the appropriate eCRF page.

Vaccines

Vaccines recommended by local guidelines should be considered. If the investigator chooses to administer a vaccine, this should be completed before first dose of study drug with appropriate precautions and time interval. It is recommended that subjects be up to date for recommended inactivated, toxoid or biosynthetic vaccines, such as injectable flu vaccine, pneumococcal, and pertussis (Tdap).

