2.4 Sample Size Determination

For the Induction Study (Part 1), approximately 462 subjects are expected to be randomized to upadacitinib 45 mg QD or placebo in a randomization ratio of 2:1. The sample size for this study is based on the expected proportion of subjects who achieve clinical remission per Adapted Mayo score at Week 8. Based on the results from Phase 2b upadacitinib Study M14-234 (Substudy 1), the proportions of subjects achieving clinical remission per Adapted Mayo score in upadacitinib 45 mg QD group and placebo

group are 19.6% and 0%, respectively. Considering the small sample size in Phase 2b study and more stringent definition of primary endpoint used for Phase 3 studies, clinical remission rate is assumed to be 5% in the placebo group and 18% in the upadacitinib 45 mg QD treatment group. Based on these assumptions, a sample size of 154 subjects in placebo and 308 subjects in upadacitinib dose will have > 95% power to detect the 13% treatment difference in the primary endpoint between upadacitinib 45 mg QD group and placebo group using two-sided Fisher's exact test at a 0.05 significant level.

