Rx Day = date of visit – date of first study drug in Substudy 1 + 1.

- a. Day of first dose of study drug in Substudy 1.
- b. Rx Day 71 or the date of the first dose of Substudy 3/Study M14-533, whichever earlier.

Rules for Efficacy Assessment Based on Concomitant Treatment

Subjects in whom the maximum steroid dose exceeds the dose used at Baseline will be considered non-responders and will be censored for efficacy assessments (i.e., they will be considered non-responders for categorical endpoints and will have Baseline values carried forward for non-categorical assessments) from that point forward through the end of the study. These subjects will continue to be evaluated in the safety analysis set.

The equivalent steroid dose will be determined based on [Table 5](#):

Table 5. Equivalent Steroid Dose

Corticosteroid	Equivalent Dose (mg)
Cortisone	25
Hydrocortisone	20
Prednisone	5
Prednisolone	5
Triamcinolone	4.0
Methylprednisolone	4.0
Betamethasone	0.75
Dexamethasone	0.75
Budesonide	1
Beclomethasone	5

Subjects in whom the following UC-related medications (oral aminosalicylates, systemic corticosteroids, and MTX) that were not being taken at Baseline and are initiated during

the study or who have dosages of these medications increased to greater than the dose taken at Baseline will be censored for efficacy assessments (i.e., will be considered non-responders for categorical endpoints and will have the last values carried forward for non-categorical assessments) from that point through the end of the study. These subjects will continue to be evaluated in the safety analysis set.

Definition of Missing Data Imputation

The following imputation methods will be used to impute missing values in the efficacy analyses. In addition, an observed case analysis will be performed.

Non-Responder Imputation (NRI)

The NRI approach is used for binary efficacy variables. These variables can take values of 'Achieved' or 'Not Achieved' or may be missing for any reason including discontinuation from study. According to the NRI imputation approach, all missing values will be considered as 'Not Achieved.'

Last Observation Carried Forward (LOCF)

For all variables (categorical variables and continuous variables), the following rules will be used for the LOCF approach:

1. Baseline and Pre-Baseline values will not be used to impute the missing Post-Baseline values.

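### Substudy 2 has no failure rule for non-steroid UC drugs started or increased before Week 8, so remission reached with added treatment can be credited to the randomised arm

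*SAP*

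**What the plan says.** Substudy 2 SAP, Section 8.2, lists the intercurrent events; they "include 1) premature discontinuation of study drug and 2) initiation or dose escalation of UC-related corticosteroids". For the first, Section 8.2.1 states "Data collected will be used regardless of premature discontinuation of study drug". For the second, Section 8.2.2 makes the subject a non-responder on binary endpoints from the event onward and drops later continuous values. Appendix E repeats this for the primary and ranked secondary endpoints. The only other route to non-response is Section 8.3.1, where Week 8 data missing for reasons other than COVID-19 count as failure.

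Protocol Section 8.1.3 sets the same rule: for Substudies 1 and 2 only a corticosteroid start or increase is a failure, and the wider rescue-medication rule is kept for Substudy 3.

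On conduct, protocol Section 5.2.3.2 states "All UC-related concomitant medications should be kept on the stable dose in Substudies 1 and 2". Section 5.2.3.3 prohibits biologics, other JAK inhibitors, thiopurines and rectal aminosalicylates. Neither section links a breach to the endpoint. Section 5.4.1 keeps subjects who stop study drug in scheduled follow-up, treated as the investigator judges best.

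**The concern.** Those provisions together leave a path to credited remission. A subject adds or increases a non-steroid UC therapy, on or off study drug, attends Week 8, and meets the remission definition. No rule removes that result, so the endpoint mixes the effect of randomised treatment with that of added therapy. The ranked secondary endpoints follow the same rule.

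The sponsor's other two SAPs in this study handle the situation differently, and the Substudy 2 SAP gives no reason for the difference. What is at stake is mainly the meaning of the Phase 3 induction estimand. The treatment difference could also shift, by an amount the documents do not let anyone calculate.

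**Working it through.** **Step 1: the three SAPs side by side.**

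| | Non-steroid UC drug started or increased | Data after study drug stops |
|---|---|---|
| Substudy 1 SAP, Section 6.0 | Non-response for oral aminosalicylates and MTX | No separate exception |
| Substudy 2 SAP, Sections 8.2 to 8.2.2 and Appendix E | No rule | All used, subject to the corticosteroid rule |
| Substudy 3 SAP, Sections 8.2.1 and 8.2.2 and Appendix E | Non-response for aminosalicylates, antibiotics and methotrexate | Used until a listed UC therapy is started or increased (biologics, JAK inhibitors, immunosuppressants, antibiotics, aminosalicylates and others) |

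The Substudy 1 rule opens "Subjects in whom the following UC-related medications (oral aminosalicylates, systemic corticosteroids, and MTX) that were not being taken at Baseline" and also covers dose increases above Baseline. Substudy 2 is the only one of the three SAPs with no non-steroid rule.

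**Step 2: reproduce the planned power.** Inputs from Substudy 2 SAP, Section 2.4: "5% in the placebo group and 18% in the upadacitinib 45 mg QD treatment group"; "a sample size of 154 subjects in placebo and 308 subjects in upadacitinib dose"; "two-sided Fisher's exact test at a 0.05 significant level". The stated result is "will have > 95% power to detect the 13% treatment difference in the primary endpoint".

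Formula: power = Σ P(X = x) P(Y = y) over all (x, y) with two-sided Fisher p ≤ 0.05, where X ~ Bin(154, 0.05) and Y ~ Bin(308, 0.18). Result: 98.9%. The stated figure is correct. Expected remitters are 154 × 0.05 = 7.7 and 308 × 0.18 = 55.4.

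**Step 3: credited remitters on placebo only.** The documents give no count of such subjects, so k is an assumption. The placebo rate becomes 0.05 + k/154, with upadacitinib held at 18%.

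| k | Placebo rate | Difference | Power |
|---|---|---|---|
| 0 | 5.0% | 13.0 points | 98.9% |
| 1 | 5.6% | 12.4 points | 97.6% |
| 2 | 6.3% | 11.7 points | 95.5% |
| 3 | 6.9% | 11.1 points | 92.3% |
| 4 | 7.6% | 10.4 points | 87.8% |

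**Step 4: credited remitters on upadacitinib only.** Now take 5% and 18% as the rates counted under the current rule, and recode a share f of the upadacitinib arm as failures. The difference under the stricter rule is 13 points minus f.

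| f | Subjects (308 × f) | Difference | Power |
|---|---|---|---|
| 1% | about 3 | 12.0 points | 97.7% |
| 2% | about 6 | 11.0 points | 95.6% |
| 3% | about 9 | 10.0 points | 92.1% |
| 5% | about 15 | 8.0 points | 79.0% |

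In this case the current rule overstates the difference. If f is equal in both arms, the difference stays at 13.0 points.

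**Step 5: robustness of the test.** At about the planning counts, 8/154 against 55/308, 22 upadacitinib remitters would have to be recoded before Fisher's p exceeds 0.05 (p = 0.056 at 22).

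**The case against.** The strongest reply is that this is a declared estimand. Substudy 2 SAP Sections 2.1 and 8.4.1 and Appendix E state it the same way, and it agrees with protocol Section 8.1.3. That stands: a reader might infer that the SAP departs from the protocol, and it does not.

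The comparison across substudies is also less clean than the table suggests. Only Substudy 3 has a rescue provision (protocol Section 5.2.3.4), so non-steroid additions are expected there. In Substudy 2 co-medication must stay stable, several of these drugs are prohibited, Part 1 lasts 8 weeks, and Week 8 non-responders are then offered open-label drug. The Substudy 1 SAP was written to Amendment 2, and its list omits antibiotics, biologics and JAK inhibitors. This stands as a reason to expect few events. It is not a reason to leave them unscored.

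The placebo scenario needs unlikely numbers. If starters remitted at 18%, three credited subjects would need 3/0.18 ≈ 17 placebo starters (11% of 154); at 5% they would need 3/0.05 = 60. Both remission rates among starters are assumptions. The 5% is itself cautious, since Section 2.4 reports 0% placebo remission in Phase 2b. From a true 0%, four credited subjects give 4/154 = 2.6%, and power stays above 99.9%.

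Existing handling covers part of the problem. Use of prohibited medication is a reportable deviation (protocol Section 7.0) and is tabulated (Substudy 2 SAP, Appendix A). Section 8.4.4 excludes subjects with deviations that could affect the primary endpoint, on criteria held in a separate classification plan. But that analysis removes subjects after randomisation instead of scoring them, and it covers the primary endpoint only. NRI-NC and HMI deal with missing data, whereas these data are observed.

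**Conclusion.** The gap is real, and closing it is a cheap improvement. As written, Week 8 remission reached after a non-steroid UC therapy was started or increased can be credited to either arm. This needs an observed Week 8 assessment and no corticosteroid event.

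Two stronger readings are tempting, and the documents support neither. The first is that the rule works against upadacitinib because uncontrolled placebo subjects are likelier to add treatment. That is plausible, but no figure in the documents shows it: crediting on placebo dilutes the effect and crediting on upadacitinib inflates it. The second is that the power statement fails. It holds at the planning rates (98.9%). It drops below 95% only if three or more credited placebo remitters (92.3% at three) come on top of a true 5%, with none on upadacitinib.

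The size of any shift in the treatment difference is unknown, because the number of such subjects is not reported. With the planned margin and an 8-week period the primary test is fairly robust, so the main issue is what the estimand means.

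**What to change.** In Substudy 2 SAP Section 8.2 and Appendix E, align the scoring with Substudy 3. Add as a failure event any start, or increase above Baseline, of an aminosalicylate, methotrexate or other immunosuppressant, UC antibiotic, biologic or other JAK inhibitor before the assessment, on or off study drug. Score binary endpoints as non-response from that date and do not use later continuous values.

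If the primary estimand is kept to match protocol Section 8.1.3, pre-specify this scoring as a sensitivity analysis of the primary and ranked secondary endpoints. Report the number of such subjects, and of remitters among them, by arm. Protocol Section 4.0 says all Substudy 2 subjects have completed induction, so if the database is already locked the analysis should be labelled post hoc.

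The cost is SAP wording and a little programming, because changes in concomitant medication are already recorded at each visit (protocol Section 5.2.3.2). The downside is a few more non-responders. The change concerns endpoint scoring only and alters no clinical management rule.
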